1.2.4. Preclinical data of ABX464

1.2.4.1. Non-clinical background information

The toxicity of ABX464 and ABX464-N-Glu was studied in a range of rodent and nonrodent species (rats, rabbits, dogs, cynomolgus and marmoset monkeys, and mini-pigs) with treatment durations ranging from 2-weeks to 6/9 months. These studies have demonstrated that ABX464 and ABX464-N-Glu are overall well tolerated. Vomiting and ptyalism were the major clinical sign, and the main target organs of ABX464 toxicity were the gastro-intestinal tract and the liver. The adverse effects noted on these organs were essentially mild/moderate but showed reversibility during the recovery phases.

Plasma exposure to ABX464 and ABX464-N-Glu in humans (based on predicted steady-state exposure in ulcerative colitis patients at the highest proposed dose of 100mg) are calculated as being approximately parity (Cmax) to 4-fold (AUC) for ABX464 and 9-fold (Cmax) to 2-fold (AUC) for ABX464-N-Glu exposure as seen in pivotal chronic toxicology studies.

ABX464 had no significant adverse effects on the nervous and respiratory systems, or on cardiovascular function. ABX464 was shown to be non-genotoxic and ABX464-N-Glu was shown to be non-mutagenic.

Genotoxicity:

ABX464 was found to be non-genotoxic. Its main metabolite, the ABX464-N-Glu was not mutagenic as assessed by an Ames test, an in vitro and an in vivo micronucleus assay.

Reprotoxicity:

Reproductive toxicity was assessed from fertility to postnatal development, in five studies. In rabbits, the maternal NOAEL was considered to be 9mg/kg od and the NOAEL for the embryo-fetal development less than 1mg/kg od. In rats, the maternal NOAEL and the NOAEL for pup development and survival is considered to be lower than 15 mg/kg od. The F1 generation NOAEL is considered to be 40mg/kg od in absence of adverse effect at this dose-level.

Teratogenicity:

ABX464 appears to have teratogenic activity.

Hepatocellular toxicity:

In minipigs the main adverse finding was centrilobular hepatocellular degeneration/necrosis associated with hemorrhage, fibrosis and /or extramedullary hematopoiesis observed at dose levels of 10mg/kg and above. The liver lesions observed in one of the animals administered 5mg/kg od, were not considered adverse. Based on this observation, the NOAEL is 5mg/kg od.

No signs of hepatotoxicity related to ABX464 have been observed in any of the patients treated with ABX464 in clinical trials and DILISym evaluation did not predict any risk of liver toxicity for ABX464 and ABX464-N-Glu.

Regarding the other observations made from the pre-clinical toxicology program, please refer to the current version of the Investigator Brochure.

1.2.5. Previous clinical experience with ABX464

The effect of ABX464 in humans has been assessed in eighteen clinical trials:

- Completed clinical studies in healthy volunteers (ABX464-001, ABX464-002, ABX464-901, ABX464-902, and ABX464-903) and controlled studies in patients with ulcerative colitis (ABX464-101 and ABX464-103), in patients with rheumatoid arthritis (ABX464-301), in HIV infected subjects (ABX464-003, ABX464-004, and ABX464-005), and in COVID-19 infected patients (ABX464-401).
- Open label studies in ulcerative colitis (ABX464-102, ABX464-104, and ABX464-108) and rheumatoid arthritis (ABX464-302).
- A drug product formulation study (ABX464-905) is ongoing in Healthy Volunteers
- A bioequivalence study (ABX464-921) is ongoing in Japanese Healthy Volunteers.

As of 30 November 2021, 1023 subjects have received ABX464, according to various administration schedules, in all completed, and ongoing open-label clinical studies across all indications. Out of these 1023 subjects, 830 subjects have been dosed with ABX464 50mg once daily (od) including 240 subjects for longer than 6 months with 197 for more than a year. In addition, 36 subjects have received ABX464 or placebo in ongoing blinded clinical study (ABX464-921). Fourteen patients have received ABX464 50mg od for more than 3 years in the UC open label maintenance study (ABX464-102) and 248 patients have received ABX464 50mg for more than 6 months.

ABX464 was rapidly absorbed in healthy volunteers, HIV and UC patients with a Cmax observed approximately 1.5 to 2.9 hours after dosing. Exposure to ABX464 was comparable in all subjects receiving ABX464 at a given dose. PK of ABX464 were linear in the dose range 50-150mg. After repeated administrations of ABX464, an initial decrease in ABX464 AUC was observed and steady state was reached after 4 weeks of treatment.

ABX464 was rapidly metabolised to ABX464-N-Glu. ABX464-N-Glu had a much longer half-life compared to ABX464 (about 100 hours) largely contributing to the high exposures observed.

Food increased ABX464 exposure at least 2.8-fold while exposure to the metabolite was comparable in fed or fasted conditions.

Clinical Efficacy

Completed and ongoing studies with ABX464 in UC are:

- Phase 2a program with an 8-week induction (ABX464-101; completed) and a 4-year maintenance (ABX464-102; ongoing; 52-week interim analysis completed) studies
- Phase 2b program including the 16-week induction (ABX464-103; completed) and an open-label extension (ABX464-104; ongoing) studies

ABX464-103 was a randomized, double-blind and placebo-controlled phase 2b induction study and was conducted from 95 centres in 16 countries. It had three once-daily oral ABX464 treatment groups (25mg, 50mg and 100mg) and one placebo group. 254 patients with moderate to severe active ulcerative colitis were enrolled into the trial. 50% of these patients had inadequate response, loss of response, or intolerance to tumor necrosis factor alpha (TNF- α) inhibitors, vedolizumab, other biologics and/or JAK inhibitors treatments while the other 50% were refractory to conventional treatments. Endoscopies were read centrally and blinded by independent reviewers. Electronic patient diaries were used to promote the reliability of the collection of stool frequency, rectal bleedings and other patient reported outcomes. Gender, clinical, biological and endoscopic parameters were well distributed across placebo and treatment groups at enrolment time. The primary endpoint, i.e. the reduction of the modified Mayo Score from baseline after 8 weeks of treatment was statistically significant for all active treatment groups. ABX464-103 study was completed in April 2021 (LPLV = 16 April 2021).

Table 01 Primary and secondary efficacy endpoints in ABX464-103 study

Week 8 top-line results (ITT ¹ population / N= 252)	Placebo	25mg	50mg	100mg
Primary Endpoint				
Modified Mayo Score	All patients	-1.9	-3.1 *	-3.2 *
Mean change from baseline	Bio exposed	-1.0	-2.8 *	-2.9 *
*p-values of <0.05 versus placebo for all dose groups (ANCOVA)				
Key Secondary Endpoints (not powered to show statistical significance)				
Endoscopic Improvement^{a,d}	All patients	8 (13.6%)	20 (34.5%) *	21 (39.6%) *
	Bio exposed	1 (3.7%)	8 (28.6%) *	7 (30.4%) *
*p-values of <0.05 versus placebo for all dose groups using a likelihood ratio chi-square test				
Clinical Remission^{b, d}	All patients	8 (12.5%)	17 (27.9%) *	11 (17.5%)
	Bio exposed	1 (3.2%)	6 (20.0%) *	2 (6.7%)
*p-values of <0.05 versus placebo using a likelihood ratio chi-square test but not according to the predefined Mantel-Haenszel Chi Square test (p<0.1)				
Clinical Response^{c, d}	All patients	23 (35.9%)	40 (65.6%) *	38 (60.3%) *
	Bio exposed	5 (16.1%)	17 (56.6%) *	13 (43.3%) *
*p-values of <0.05 versus placebo using a likelihood ratio chi-square test				
Fecal Calprotectin (µg/g)	All patients	-1027.7	-2192.8 **	-2316.8 **
Mean change from baseline				-2280.9 **
**p-values of <0.01 versus placebo (MMRM)				
1 = Intent-to-treat patient population. Drop-out patients were considered as failure for all binary endpoints. Nearest neighbor imputation (as defined in the Statistical Analysis Plan) was used for missing values at week 8 and applied to MMS, clinical remission, and clinical response. Endoscopic improvement rates are presented without imputation (data available at time point).				
a = Endoscopic improvement is defined as endoscopic subscore ≤1.				
b = Clinical remission (per Modified Mayo Score) is defined as stool frequency subscore (SFS) ≤1, rectal bleeding subscore (RBS) of 0 and endoscopic subscore ≤1.				
c = Clinical response (per Modified Mayo Score) is defined as a decrease from baseline in the Modified Mayo Score ≥2 points and ≥30% from baseline, plus a decrease in RBS ≥1 or an absolute RBS ≤1.				
d = Evidence of friability during endoscopy confers an endoscopic subscore of 2 or 3				

ABX464 was shown to be effective in patients refractory to conventional treatments and, importantly, also in patients with inadequate response, loss of response, or intolerance to biologics and/or JAK inhibitors. These efficacy results warrant the continuation of the development of ABX464 in UC indication.

97.7% of all patients who completed the phase 2b induction study (ABX464-103), irrespective of treatments or treatment outcome during the induction study, enrolled into this subsequent open-label maintenance study to evaluate the long-term safety and efficacy profile of ABX464 for up to two years.

Clinical Safety

During non-clinical studies, the main clinical signs observed in non-clinical studies for ABX464 consisted of, ptalism and bodyweight loss which was dose proportional and severe in some cases. the main target organs affected were the gastro-intestinal tract and liver with the main macroscopic findings observed as dark foci in the glandular mucosa of stomach, adverse altered cell foci and bile duct hyperplasia in the liver, adverse erosion/ulcer in the forestomach, centrilobular hepatocellular degeneration/necrosis and liver necrosis. Some degree of anemia was found in the 9-month marmoset study with ABX464-N-Glu. Immunosuppression has been observed in a 9-month study with direct dosing of ABX464-N-Glu in cynomolgus monkeys. Two cases of cardiac fibrosis, likely associated with the Marmoset Wasting Syndrome, have been observed in a 9-month study with marmoset monkeys exposed to high doses of ABX464-N-Glu.

As of 30 November 2021, 1023 subjects have received ABX464, according to various administration schedules, in all completed, and ongoing open-label clinical studies across all indications. Out of these 1023 subjects, 830 subjects have been dosed with ABX464 50mg once daily (od) including 240 subjects for longer than 6 months with 197 for more than a year. In addition, 36 subjects have received ABX464 or placebo in the ongoing blinded clinical study (ABX464-921). All doses tested were well tolerated. 38 Serious Adverse Events were reported in all clinical studies, except COVID study (ABX464-401) which are reported separately in this IB. No fatalities were reported in non-COVID indication/population except one fatal case that was a road traffic accident and was unrelated to the study drug.

Anticipated ABX464 adverse events (regardless of their severity)

Frequent gastrointestinal symptoms such as abdominal pain, nausea, vomiting and diarrhea, as well as headaches, are described effects for ABX464, which are dose-dependent, with intensity going from mild to severe, occurring after treatment onset.

Therefore, designated anticipated AEs are:

- Headache
- Nausea
- Vomiting
- Abdominal pain (abdominal pain or upper abdominal pain)
- Diarrhea
- Back pain

Due to safety signals in nonclinical toxicology studies, the following events are monitored as adverse events of special interest in ongoing and future studies with ABX464: anemia, liver function tests abnormalities, serious grade 3 infections and opportunistic infections, malignancies including non-melanoma skin cancers and cardiac events, including biomarkers (blood levels of AST, troponin, CPK and NT-proBNP).

The following events have been observed in clinical studies and are also monitored as adverse events of special interest in ongoing and future studies with ABX464: headaches, skin lesions plus lipase elevation and acute pancreatic disorders.

Healthy volunteers and patients exposed to ABX464 will continue to be monitored with routine ECGs as part of the clinical studies.

Overall, ABX464 is considered to be safe and clinical development is justified.

For further information, please refer to the current Investigator's Brochure.

1.3. Rationale for the clinical study and study design

Phase IIb study (ABX464-101) aimed at evaluating the efficacy and safety of ABX464 given at a fixed dose of 50mg once daily versus placebo in patients with moderate to severe active UC who have failed or are intolerant to immunomodulators, anti-TNF α or corticosteroids was conducted in Belgium, France, Germany, Austria, Poland, Hungary.

32 patients were randomized (23 ABX464 patients/9 placebo). The principal study results are presented below.

A strong efficacy signal was observed with ABX464 50 mg:

- Clinical Remission rate of 35.0 % of ABX464 patients (Placebo = 11.1%)
- Mucosal Healing rate of 50.0 % (p=0.03) of ABX464 patients (Placebo = 11.1%)
- Clinical Response rate of 70.0 % of ABX464 patients (Placebo = 33.0%)

Same results were also observed in Total and Partial Mayo Score, as depicted in the following graphs

[figure not shown]

Figure 3: Mean change in Total and Partial Mayo Score in ABX464-101 study

At the end of the completed 2 months induction treatment study, 22 Patients (15 previously treated with ABX464 and 7 on placebo) were enrolled into the open-label maintenance study with ABX464 50mg daily (ABX464-102) regardless of what treatment they had previously received. An interim analysis of this maintenance study was performed after all patients had completed at least 12 months dosing in the maintenance study, with a mean ABX464 treatment duration in the maintenance study of 422 days.

The interim analysis used the Month 12 Per Protocol (M12 PP) dataset which included all subjects that had a Month 12 visit. Of the 22 subjects, 3 subjects were excluded from the M12 PP Set: 2 subjects from the ABX464 induction group (one who withdrew due to lack of efficacy at M1 of the maintenance study and one who was lost to follow-up) and 1 subject from the placebo induction group (grade 2 headache at month 4), resulting in 19 subjects analyzed in the efficacy M12 PP set at baseline. Of the nineteen subjects in the set, sixteen had had a Month 12 endoscopy performed which forms part of the Total Mayo score (TMS).

Clinical remissions obtained at the end of the induction study were durable and the rates further improved during the maintenance phase, as additional subjects achieved clinical remission for 12 months treatment.

All patients who had an endoscopy performed, had an endoscopic sub-score of 0 or 1. 12/16 patients were in clinical remission at month 12.

Mean and median fecal calprotectin and CRP showed continued declines during the maintenance study, though the large variability and small patient numbers requires that the results should be interpreted with caution. The measurement of miR124 relative gene expression by qPCR using whole blood samples was included in both ABX464-101 and -102. A total of 19 patients were sampled on day 0, 28, 56 of ABX464-101 and on day 365 (while in ABX464-102). Statistically significant increases of miR124 expression were observed at all these time points.

No severe or serious adverse reactions were reported. Most adverse events were of mild to moderate intensity. The efficacy and safety results of studies ABX464-101 and ABX464-103 warrant the continuation of the clinical development of ABX464 in this indication.

2. STUDY OBJECTIVES AND ENDPOINTS

2.1. Primary Objective

The primary objective of the study is to evaluate the long-term safety of ABX464 given at 50 mg once daily in subjects with Moderate to Severe Active Ulcerative Colitis.

2.2. Secondary Objectives

The secondary objectives are:

- To evaluate the long-term effect of ABX464 on clinical and endoscopic remission in subjects with Moderate to Severe Active Ulcerative Colitis assessed by the MCS.
- To evaluate the long-term effect of ABX464 on inflammatory markers (CRP, Calprotectin and ESR)
- To evaluate the long-term of ABX464 on Quality of Life (QoL) measured by the SF-36 questionnaire in subjects with Moderate to Severe Active Ulcerative Colitis until M24.

Echocardiography objective is:

- To evaluate the effect of ABX464 on cardiac function as assessed through echocardiograms.

2.3. Primary Endpoint

The primary endpoint of this study is defined as the number of incidences of treatment-emergent adverse events in the ABX464 treated subjects.

2.4. Secondary Endpoints

The secondary endpoints of this study are:

- The change from Day 0 in Total Mayo Score.
- The change from Day 0 in Partial Mayo Score.
- The time to UC worsening.
- The change from Day 0 in fecal calprotectin, CRP levels and ESR.
- The scores and changes from Day 0 in SF-36 Questionnaire scores.
- The miR-124 expression at month 12, month 36 and month 48.
- The number of incidences of treatment-emergent serious adverse events.
- The number of incidences of treatment-emergent adverse events of special interest.
- The number of incidences of adverse events leading to investigational product discontinuation.
- The number of incidences of specific laboratory abnormalities.
- Percentage of subjects reaching clinical remission at M12, M36, and M48.
- Percentage of subjects reaching clinical response at M12, M36, and M48.
- Percentage of subjects reaching endoscopic improvement at M12, M36, and M48.
- Percentage of subjects reaching endoscopic remission at M12, M36, and M48.
- Percentage of subjects reaching corticosteroid-free clinical remission at M12, M36, and M48.

The echocardiography secondary endpoints^[9] are:

- Absolute (%) change-from-previous echocardiogram of Left ventricle Ejection Fraction (LVEF) as measured by 2-dimensional echocardiography
- Number of subjects with a clinically relevant reduction (change-from-previous echocardiogram) of LVEF, defined as by > 10% reduction (absolute percentage points) to a value < 50%

- Absolute (%) change in Global Longitudinal Strain (GLS) from-previous echocardiogram
- Number of subjects with a relative percentage reduction in GLS by > 15% from the previous value
- Number of subjects with a reduction of LVEF > 10% (absolute percentage points) to a value $\geq 50\%$ with an accompanying fall in GLS > 15%
- Number of subjects with reduction in LVEF by > 10% (absolute percentage points) to a value $\geq 50\%$
- Changes from previous echocardiography of other echocardiographic parameters as described in a standard protocol, including 2-dimensional volumes, RV size and systolic function and valve function.

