	
The echocardiography objective is:
 
To evaluate the effect of ABX464 on cardiac function as assessed through echocardiograms.
		
Study Endpoints	
Primary Endpoint:
 
 ▪ Number of incidences of treatment-emergent adverse events in ABX464 treated subjects. 
Secondary Endpoints:
 
 ▪ The change from Day 0 in Total Mayo Score. ▪ The change from Day 0 in Partial Mayo Score. ▪ The time to UC worsening. ▪ The change from Day 0 in fecal calprotectin, CRP levels and ESR. ▪ The scores and changes from Day 0 in SF-36 Questionnaire scores. ▪ The miR-124 expression at month 12, month 36 and month 48. ▪ The number of incidences of treatment-emergent serious adverse events. ▪ The number of incidences of treatment-emergent adverse events of special interest. ▪ The number of incidences of adverse events leading to investigational product discontinuation. ▪ The number of incidences of specific laboratory abnormalities. ▪ Percentage of subjects reaching clinical remission at M12, M36, and M48. ▪ Percentage of subjects reaching clinical response at M12, M36, and M48. ▪ Percentage of subjects reaching endoscopic improvement at M12, M36, and M48. ▪ Percentage of subjects reaching endoscopic remission at M12, M36, and M48. ▪ Percentage of subjects reaching corticosteroid-free clinical remission at M12, M36, and M48. 
The echocardiography secondary endpoints are:
 
 ▪ Absolute (%) change-from-previous echocardiogram of Left ventricle Ejection Fraction (LVEF) as measured by 2-dimensional echocardiography ▪ Number of subjects with a clinically relevant reduction (change-from-previous echocardiogram) of LVEF, defined as by > 10% reduction (absolute percentage points) to a value < 50% ▪ Absolute (%) change in Global Longitudinal Strain (GLS) from-previous echocardiogram ▪ Number of subjects with a relative percentage reduction in GLS by > 15% from the previous value ▪ Number of subjects with a reduction of LVEF > 10% (absolute percentage points) to a value ≥ 50% with an accompanying fall in GLS > 15% ▪ Number of subjects with a reduction in LVEF by > 10% (absolute percentage points) to a value ≥ 50% ▪ Changes from previous echocardiography of other echocardiographic parameters as described in a standard protocol, including 2-dimensional volumes, RV size and systolic function and valve function. 		

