5.3. Detail of the study assessments

5.3.1. Echocardiography

Since enrolment is completed at the time of this amendment, drug-free baseline measurements are not available.

All patients ongoing in the study have already undergone Month 36 visit. Therefore, an echocardiography will be performed at the earliest visit and then at Month 42 and Month 48. Echocardiography will be performed locally. Procedures will be standardized for optimized video acquisition at clinical sites. Sites will receive an Echocardiography Manual that includes detailed instructions regarding image acquisition.

Two-dimensional echocardiography measurements will be assessed during the study. The following standard parameters - pertinent to the assessment of changes in cardiac function will be assessed:

- Left Ventricular Ejection Fraction (LVEF%)
- Left Ventricular end systolic/end diastolic volumes
- Left Ventricular septal/posterior wall thickness
- Left Ventricular Mass/Mass indexed
- Left Ventricular Global Longitudinal Strain (GLS)
- Left Atrial volume
- Doppler assessment (Mitral E/A ratio, Stroke Volume, Cardiac Output, Tissue Doppler Imaging)
- Valvular assessment for regurgitation/stenosis
- Right ventricular size

Specific attention will be brought to potential changes from previous assessment in LVEF and GLS. All echocardiographic parameters will be presented descriptively and will be reviewed by the Independent Cardiovascular Safety Committee (ICVSC).

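### No echocardiography endpoint is defined against the first on-study echo, so with three echoes a stepwise fall of up to 20 LVEF points or about 28% in GLS can escape the threshold counts

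*Protocol*

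**What the plan says.** Protocol 2.4, repeated in the synopsis, lists seven echocardiography secondary endpoints. Five name the previous echo as reference:

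- LVEF change: "Absolute (%) change-from-previous echocardiogram of Left ventricle Ejection Fraction (LVEF) as measured by 2-dimensional echocardiography"
- LVEF fall to below 50%: "Number of subjects with a clinically relevant reduction (change-from-previous echocardiogram) of LVEF, defined as by > 10% reduction" (in absolute percentage points)
- GLS change: "Absolute (%) change in Global Longitudinal Strain (GLS) from-previous echocardiogram"
- GLS fall: "Number of subjects with a relative percentage reduction in GLS by > 15% from the previous value"
- other parameters: "Changes from previous echocardiography of other echocardiographic parameters as described in a standard protocol"

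Two name no reference echo. One begins "Number of subjects with a reduction of LVEF > 10% (absolute percentage points) to a value" and requires a final value of at least 50% together with a GLS fall above 15%. The other begins "Number of subjects with reduction in LVEF by > 10% (absolute percentage points) to a value" and has the same 50% condition without the GLS part.

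On timing, Protocol 5.3.1 says: "Therefore, an echocardiography will be performed at the earliest visit and then at Month 42 and Month 48". It also records that no drug-free baseline echo exists and that all ongoing patients have passed Month 36. SAP 1.2, 2.2 and 4.2 move the echo endpoints to a separate report, and the SAP defines no reference echo for them.

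**The concern.** The echo objective is the effect of ABX464 on cardiac function in a long-term safety study. A slowly accumulating effect would appear as a gradual decline, and a rule that looks only one echo back is weakest for that pattern. A subject can lose a substantial amount of LVEF or GLS in two moderate steps without either step crossing its threshold.

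The missing drug-free baseline explains why a true baseline comparison was not planned. It does not explain why the first available echo is not used as a fixed on-treatment reference. Elsewhere the protocol does use fixed references: Day 0 for the Mayo, biomarker and SF-36 changes (2.4), and baseline values for the cardiac laboratory parameters (8.2).

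**Working it through.** The plan gives no figure on this point to reproduce, so the check works from its thresholds and schedule.

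**Inputs from the documents.** LVEF threshold: more than 10 absolute points. GLS threshold: more than 15% relative. Echoes per subject: at most three, so at most two successive comparisons.

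**Largest fall with no step over the threshold,** for k echoes (GLS taken as magnitude):

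- LVEF: 10 × (k − 1). For k = 3 this is 20 points. For k = 2 it is 10 points.
- GLS: 1 − 0.85^(k − 1). For k = 3 this is 1 − 0.7225 = 27.75%. For k = 2 it is 15%.

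With two echoes the previous echo is also the first, so there is no gap. With the first echo as an added reference, the largest uncounted fall is 10 points or 15%, however many echoes there are.

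**Worked paths**

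| Path | Each step | First to third | Counted against previous echo | Counted against first echo |
|---|---|---|---|---|
| LVEF 65, 56, 47 | 9, 9 | 18, to below 50% | no | yes |
| LVEF 60, 50, 40 | 10, 10 | 20, to below 50% | no | yes |
| LVEF 70, 60, 50 | 10, 10 | 20, to 50% | no | yes |
| GLS 20, 17, 14.45 | 15%, 15% | 27.75% | no | yes |

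**Effect of the two endpoints with no stated reference.** Both need a final value of at least 50%. For 65, 56, 47, the second echo is down only 9 points and the third is below 50%, so neither endpoint counts this subject under any reference. The same holds for 60, 50, 40. For 70, 60, 50 the reading matters: against the first echo it would be counted. The LVEF and GLS counts are separate, so a 20-point LVEF fall escapes all of them only if GLS also stays within 15% at each step.

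**Simulation.** All of these inputs are assumptions, because the documents give none: starting LVEF 62, independent normal measurement error, SD 3 to 5 points, three echoes. The falls occur in two equal steps.

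| Scenario | Count | Previous echo only | First echo added |
|---|---|---|---|
| True fall of 15 points | fall > 10 | 53–66% | 82–89% |
| True fall of 15 points | fall > 10 to < 50% | 33–49% | 71–81% |
| True fall of 5 points, SD 3 | fall > 10 to < 50% | 0.6% | 1.0% |
| No true change, SD 3 | fall > 10 | 1.9% | 2.6% |
| No true change, SD 5 | fall > 10 | about 16% | about 19% |

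GLS was not simulated.

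**The case against.** A reader might infer that every echo endpoint uses the previous echo and that a gradual fall would never be flagged. The documents do not support that, for four reasons.

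1. **Two endpoints state no reference.** Reading them as previous-echo is an inference from their neighbours and from Protocol 5.3.1, which draws attention to changes from the previous assessment. This stands.

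2. **Other routes exist.** Protocol 9.3 tabulates subjects with at least one abnormal value, in a paragraph that names echo parameters. Left ventricular systolic dysfunction and heart failure are cardiac adverse events of special interest with no step threshold (8.2). SAP Listing 16.2.8.6 shows echo results by visit with an interpretation, and the Independent Cardiovascular Safety Committee reviews all echo parameters (5.3.1). If *abnormal* meant LVEF below 50% (an assumption), a simple count of any such value would catch 78–85% in the 15-point scenario. The first-echo version of the below-50% count catches 71–81%. So *never flagged* is too strong. But no abnormal limit for LVEF or GLS is given, an abnormal value is not a measure of decline, and SAP 14.1 lists no echo table. The continuous endpoints show each step separately, so no planned output reports a subject's cumulative change.

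3. **Few subjects may have three echoes.** The synopsis ends the study in Q3 2022, so the last Month 48 visit falls by about 30 September 2022. The last Month 39 visit then falls by about 30 December 2021, or 13 January 2022 with the 14-day window. The SAP cites protocol Version 7.0 of 7 February 2022. If that version introduced echocardiography, first echoes fall at Month 42 or later and at most two fit. The documents do not show which version did so, so the number with three echoes is unknown and could be none.

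4. **The simulated gain depends on a large assumed fall.** A 15-point loss must occur between an echo after Month 36 and Month 48. For a 5-point fall the gain in the below-50% count is negligible. These are also descriptive endpoints in a small group: Protocol 1.2.5 reports fourteen patients treated for more than three years in this study.

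Points 3 and 4 limit the importance of the gap; they do not close it.

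**Conclusion.** The concern holds in a limited form. No echo endpoint is defined against the first on-study echo, and two endpoints do not say what they are compared with. For a subject with three echoes, and the previous echo as reference throughout, a stepwise fall of up to 20 LVEF points (with GLS within 15% per step) or about 28% in GLS can escape the threshold counts. For LVEF falls ending below 50%, such as 65, 56, 47, that does not depend on how the two unspecified LVEF endpoints are read. The maxima are arithmetic on the plan's own thresholds; the detection and false-flag rates rest on the assumed LVEF level, fall and SDs.

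It would go too far to conclude that a cumulative decline would go unseen, or that all subjects are exposed to the gap. Subjects with two echoes are unaffected, and the other safety outputs may bring such a fall to light without measuring it. This is a cheap improvement to the echo report, not a fault that undermines the study. The separate report's plan is not among the documents and may already include the comparison.

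**What to change.** In Protocol 2.4, the synopsis and the plan for the separate echo report:

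1. State the reference echo for all seven endpoints, including the two LVEF counts that end at 50% or above.
2. Add each LVEF and GLS change and threshold count against the first on-study echo, with the thresholds unchanged. Label it as an on-treatment reference and show it beside the previous-echo result.
3. Report how many subjects have two echoes and how many have three, since the two references differ only at the third echo.

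The cost is wording and one extra derived variable, with no additional echo or visit. The downside is the small rise in false flags shown in the no-change rows above; presenting the two counts side by side lets the reader see its effect.
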